6.5 CONCOMITANT THERAPY

Therapy prior to enrollment with any other experimental treatment or off-label use of marketed medications that are intended as specific treatment for SARS-CoV-2 infection (i.e., post-exposure prophylaxis) are permitted.

Participants who are taking remdesivir for COVID-19 or another antiviral for a concurrent infection (e.g. oseltamivir for an influenza virus, lopinavir/ritonavir for HIV, etc.), or

immunosuppressive drugs for other medical conditions (corticosteroids for an unrelated condition, tocilizumab for rheumatoid arthritis, hydroxychloroquine for lupus, etc.) may continue with the treatment.

Participants entering the trial may be prescribed therapy for SARS-CoV-2 that has received preliminary FDA approval whether available by prescription or under an expanded access program (EAP), e.g. remdesivir or dexamethasone. These medications may be initiated or continued. However, participants may not have previously received or be given SARS-CoV-2 convalescent plasma under the Mayo or any other EAP.

A participant cannot participate in another clinical trial for the treatment of SARS-CoV-2 until after Day 29. However, if the participant has progressed to respiratory failure in the hospital (see definition in *Section 3*), another experimental treatment protocol may be initiated, but only if there is a sponsor-approved agreement between the leadership of both trials. The agreement will consider potential impact of dual enrollment on study outcomes and participant safety and establish procedures to coordinate adverse event monitoring and reporting of dual-enrolled participants.

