8.2 BASELINE, RANDOMIZATION AND PRODUCT ADMINISTRATION

Baseline assessments should be performed before the first study product administration.

The following eligibility/baseline assessments can be done up to 72 hours prior to randomization time: demographic information (age, ethnicity, gender, body mass index), medical history/baseline comorbidities (e.g. obesity, smoking, diabetes, hypertension, cardiac, renal, liver, and lung disease), and physical exam.

Baseline clinical status data are collected right before randomization. Baseline vital signs (NEWS2) should be collected closest to randomization time and must be collected within 24 hours prior to randomization time.

The following additional baseline assessments are collected prior to study product administration:

- COVID-19 signs and symptoms, including day of onset,
- Medications for this current illness taken in the 7 days prior to Day 1 (See Section 6.5),
- Designated pre-admission medications by class (See Section 6.5),
- Adverse events (See Section 8.5),
- Safety and research labs (See Section 8.4).

Day 1 safety and research labs should be collected up to 24 hours prior to randomization and before first study product administration. Laboratory tests performed as part of routine clinical care within the same time period will be accepted for Day 1 safety laboratory tests.

Ideally, product administration should start on the same day as randomization (Day 1), but may be started up to 36 hours after randomization.

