8.3.3 NATIONAL EARLY WARNING SCORE 2 (NEWS2)

The NEWS2 point score (<https://www.mdcalc.com/national-early-warning-score-news-2>)⁴³ will be used (see **Table 4, Section 3, Objectives and Endpoints**):

- 1) to assess the severity of illness and comparability of subjects in the convalescent plasma and control groups at enrollment, and
- 2) to compare changes in score over time between the two groups. Patients who die will be coded on their values on the day of death if the values are available.

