2.2 SAMPLE SIZE DETERMINATION

Primary endpoint

The Chi-square test will be used to compare treatment arms on the proportion of death from any cause or respiratory failure up to and including Day 28, with two-sided significance level = 0.05.

A meta-analysis of studies of SARS coronavirus infection and severe influenza reported that convalescent plasma led to an absolute reduction in the risk of mortality from 7% to 23% and a 54% greater likelihood of discharge by day 22²⁵. These data suggest that the treatment benefit of convalescent plasma in reducing the risk of death and respiratory failure may be substantial, particularly early in hospitalization. For this trial we conservatively assume a 10% absolute reduction (30% in the control group and 20% in the convalescent plasma group) given that this trial allows local standard of care in both arms, which may include effective medications for COVID-19.

Table 6. Required number of participants to have 80%, 85% or 90% power for the primary outcome, assuming no missing data.

Proportion in the control group	Absolute reduction	Corresponding proportion in the plasma group	Number of participants needed		
			80% power	85% power	90% power
35%	11%	24%	532	610	712
	10%	25%	652	746	874
	9%	26%	858	976	1134
	8%	27%	1042	1192	1396
30%	11%	19%	474	542	634
	10%	20%	582	666	778
	9%	21%	730	834	976
	8%	22%	936	1072	1254
25%	11%	14%	400	458	536
	10%	15%	496	566	662
	9%	16%	624	714	836
	8%	17%	806	922	1080

Table 6 provides the total number of participants needed for 80%, 85% or 90% power to detect a range of differences in the primary outcome, using the z-test with a two-sided significance level = 0.05 and assuming no missing data. A total of 666 participants are needed to have 85% power for a 10% absolute reduction when the proportion of death or respiratory failure is 30% in the control group (**Table 6**). This sample size has 76% power to detect a 9% absolute reduction

when the control rate is 30% and has 90% (81%) power to detect a 10% absolute reduction when the control rate is 25% (35%) (**Table 7**).

Table 7. Power of a study of 666 participants to detect differences in the primary outcome, assuming no missing data.

Proportion in the control group	Absolute reduction	Corresponding proportion in the convalescent plasma group	Power
35%	11%	24%	88%
	10%	25%	81%
	9%	26%	72%
	8%	27%	61%
30%	11%	19%	91%
	10%	20%	85%
	9%	21%	76%
	8%	22%	66%
25%	11%	14%	95%
	10%	15%	90%
	9%	16%	83%
	8%	17%	72%

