2.4.2 ANALYSIS OF THE PRIMARY EFFICACY ENDPOINT(S)

The primary efficacy analysis to compare the proportion of death or respiratory failure by Day 28 will be done by the Chi-square test. Difference in the proportions and the 95% confidence interval will be presented. To account for randomization stratification factors, site and age (≥ 65 vs < 65 years old), we will use a logistic regression model with site and age as covariates, or as random effects in a generalized linear mixed effects model. We will also perform regression analyses to adjust for baseline patient characteristics (including age, sex, race, Hispanic ethnicity, ABO blood type, BMI, hypertension, chronic lung, heart or kidney diseases, diabetes, immunosuppression). Odds ratios and 95% confidence intervals will be provided.

Every attempt will be made to obtain outcome data for all participants. While we anticipate minimum loss of follow-up in this short follow-up study, small amounts of missing primary outcome data may occur. In such cases, subjects without the primary outcome data will be excluded from the primary analysis. Sensitivity analyses will evaluate the impact of making different assumptions about missing observations and use analysis methods such as multiple imputations. These analyses will be defined in the Statistical Analysis Plan.

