2.4.3 ANALYSIS OF THE SECONDARY ENDPOINT(S)

Key secondary endpoint, time to recovery:

The primary analysis for time to recovery by Day 28 is an unadjusted log-rank test. Deaths will be considered as never recovering and censored at Day 28. Kaplan-Meier curves and 95% confidence bounds will be provided. If data permit, we may perform a stratified log-rank test where stratification is according to participating site and age (≥ 65 vs < 65 years old), i.e. site and age are randomization stratification factors. We will also perform Cox regression to adjust for baseline patient characteristics (including age, sex, race, Hispanic ethnicity, BMI, hypertension, chronic lung, heart or kidney diseases, immunosuppression). Recovery rate ratio and 95% confidence interval will be provided.

Other secondary endpoints:

- 1) Binary data (e.g., 28-day mortality) will be summarized as a percent with 95% confidence intervals. Comparisons between arms will be presented as differences in proportions with 95% confidence intervals.
- 2) The ordinal scale of patient clinical status will be used to estimate a proportional odds model. The hypothesis test will perform a test to evaluate whether the common odds ratio for treatment is equal to one. If data permit, a test stratified by site will also be performed. The distribution of severity results will be summarized by treatment arm as percentages. Efforts to minimize loss-to-follow-up will be considerable. However, small amounts of missing data may occur. In such cases, subjects without final outcome data will be excluded from the analysis. Sensitivity analyses will evaluate the impact of making different assumptions about missing observations. These analyses will be defined in the Statistical Analysis Plan.
- 3) Differences in time-to-event endpoints (e.g., time to respiratory failure or death and time to at least a one category improvement in the ordinal scale) by treatment will be summarized with log-rank tests, Kaplan-Meier curves and 95% confidence bounds. The same procedure will be used to compare time to at least a two-category improvement. Hazard ratios (for time to respiratory failure or death) or improvement rate ratios (for time to improvement) and 95% confidence intervals will be provided.
- 4) Change in ordinal scale at specific time points will be summarized by proportions (e.g., proportion who have a 1-, 2-, 3-, or 4-point improvement or 1-, 2-, 3-, 4-point worsening).

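### The adjusted models for the primary endpoint and time to recovery name no measure of entry severity or background COVID-19 therapy, although baseline NEWS2 and prior medications are collected

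*Combined protocol and SAP*

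**What the plan says.** **Background therapy.** Section 6.5 lets participants receive COVID-19 therapies, "e.g. remdesivir or dexamethasone. These medications may be initiated or continued". The sample size section (9.2, printed 2.2) justifies its effect size on the ground that "this trial allows local standard of care in both arms, which may include effective medications for COVID-19".

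**What is collected before treatment.** Section 8.2 lists "Medications for this current illness taken in the 7 days prior to Day 1", requires vital signs for NEWS2 within 24 hours before randomisation, and has clinical status recorded just before randomisation. Section 8.3.3 gives baseline NEWS2 a purpose: "to assess the severity of illness and comparability of subjects in the convalescent plasma and control groups at enrollment".

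**What the models name.** The primary test in 9.4.2 is a Chi-square test. It is supplemented by a logistic model with site and age, and by regressions adjusted for further characteristics, "including age, sex, race, Hispanic ethnicity, ABO blood type, BMI, hypertension, chronic lung, heart or kidney diseases, diabetes, immunosuppression". For time to recovery (9.4.3, printed 2.4.3) the test is an unadjusted log-rank, supplemented by a Cox model with covariates "including age, sex, race, Hispanic ethnicity, BMI, hypertension, chronic lung, heart or kidney diseases, immunosuppression".

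**Elsewhere.** Randomisation is stratified by site and age (6.3.1). The four subgroups in 9.4.7 are symptom duration, comorbidity count, age and BMI. The exploratory modifiers in 9.4.8 are race, ethnicity and ABO type. None of these is entry severity or background COVID-19 therapy.

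**The concern.** The endpoint is ventilation, ECMO or death, in patients who already need oxygen. How ill they are at entry is an obvious prognostic factor, and the protocol supports this: Section 3 says NEWS2 discriminates patients at risk of poor outcomes. The Background (Introduction, 2.2) says remdesivir shortened time to recovery, which is the key secondary endpoint, but the Cox model for that endpoint does not name it. Section 9.4.3 also recognises that unequal receipt of other SARS-CoV-2 treatments can affect interpretation. The sensitivity analyses it plans, however, cover only enrolment in another trial after respiratory failure.

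What is at stake is the supportive evidence. If the arms differ by chance in severity or background drugs, readers will look to the adjusted estimates for reassurance, and the named covariates would not provide it. Adding severity only after an imbalance has been seen would be a data-driven choice.

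**Working it through.** **1. The plan's own figure.** Inputs from 9.2: a test "with two-sided significance level = 0.05"; "conservatively assume a 10% absolute reduction (30% in the control group and 20% in the convalescent plasma group"); 85% power; 1:1 allocation from 6.3.1.

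- n per arm = (1.960 + 1.036)² × (0.30×0.70 + 0.20×0.80) / 0.10² = 8.98 × 37 = 332.2, rounded up to 333, so 666 in total, as stated.
- Standard error of the risk difference = √(0.37/333) = 0.0333, or 3.3 points.
- Power = Φ(0.10/0.0333 − 1.96) = Φ(1.04) = 85%, as stated. A pooled-variance calculation gives 84.8%.

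This is the power of the unadjusted test. Adding covariates to a supportive model does not alter it.

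**2. Size of a chance imbalance in severity.** The documents give no prognostic strength, so this is assumed: half the participants are at higher risk, with control risks of 45% vs 15% (or 40% vs 20%), each averaging 30%.

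- SD of the between-arm difference in the higher-risk share = √(0.25 × 2/333) = 0.0387, or 3.9 points.
- Shift in the risk difference at 1 SD: 0.0387 × 0.30 = 1.2 points (0.0387 × 0.20 = 0.8).
- At 2 SD: 2.3 points (1.5).
- Share of sampling variance: (1.16/3.33)² = 12%, or (0.77/3.33)² = 5%. It is a component of the 3.3-point standard error, not an addition to it.

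**3. The same for a baseline drug.** Assume 10% to 90% of participants use it and it changes event risk by 5 to 15 points.

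- 95% range of the between-arm difference in use = 1.96 × √(q(1−q) × 2/333): ±4.6 points at q = 0.1 or 0.9, and ±7.6 points at q = 0.5.
- Shift in the risk difference at that limit: from 0.046 × 5 = 0.2 points to 0.076 × 15 = 1.1 points.

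**4. What naming severity could add to the adjusted logistic model.** A simulation used 1,500 trials per setting, 333 per arm and marginal risks of 30% vs 20%, with a severity score of assumed strength. It gave the following power for the treatment term:

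| Odds ratio per SD of severity | Unadjusted | Adjusted |
|---|---|---|
| 1.5 | 85% | 86% |
| 2.0 | 85% | 88% |
| 2.5 | 85% | 90% |

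Simulation error is about √(0.85×0.15/1500) = 0.9 points. The comparison is with no adjustment at all. The plan already adjusts for age, BMI and comorbidities, so where these overlap with severity the added gain is smaller. In a logistic model the gain appears as a stronger test of a conditional odds ratio further from 1, not as a narrower interval on the same quantity.

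**5. What a background-therapy subgroup could show.** With an even split, the interaction standard error is 2 × 3.33 = 6.7 points. For a 10-point difference in effect, 10/6.67 = 1.5, and power is P(Z > 1.96 − 1.5) = 32%. For 80% power the difference must be (1.96 + 0.84) × 6.67 = 18.7, about 19 points. An uneven split is worse.

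**The case against.** The strongest reply is that nothing decisive is affected. The deciding tests are unadjusted, and randomisation protects them. The lists begin with *including*, so they are open, and 9.4.1 promises a statistical analysis plan before unblinding. Imbalance would also be seen: NEWS2 is assigned to check comparability, 9.4.5 tabulates baseline characteristics by arm, and the DMC monitors comparability (9.4.6.3). All of this stands, and it limits the point to naming variables in supportive models. Seeing an imbalance, though, is not the same as having a pre-named model to respond with.

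A reader might infer more than the documents support:

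- *That the trial loses power.* The gains in step 4 belong to an adjusted analysis; the Chi-square test decides the trial.
- *That baseline WHO score or oxygen flow should be added.* Inclusion criterion 6 requires cannula or mask oxygen and bars heated high-flow at 15 Lpm or more, so nearly everyone enters at score 4. NEWS2 codes oxygen only as air or oxygen. The protocol mentions oxygen requirement but does not show that flow rate is recorded.
- *That sicker patients are the ones given steroids.* The documents do not say who receives them.
- *That a subgroup would settle whether plasma adds to these drugs.* By step 5 it largely could not. The plan's question is plasma against saline on top of local care.

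**Conclusion.** The point holds in limited form. Neither model names entry severity or pre-randomisation COVID-19 therapy, although suitable baseline values are collected and the protocol itself describes NEWS2 as prognostic and remdesivir as shortening recovery. The case for the corticosteroid term is weaker on the documents: it rests on Section 6.5 naming dexamethasone and on the general remark in 9.2 about effective background drugs.

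The primary and key secondary tests are not biased, and their type I error and power are unchanged. The cost is lower efficiency in the adjusted analyses, by at most a few points of power under the assumptions in step 4, and no planned demonstration that the result withstands a chance severity imbalance. Such an imbalance could move the risk difference by roughly 1.5 to 2.3 points at 2 SD. These sizes rest on assumed prognostic strengths; the absence of the variables from the lists is read directly from the text.

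**What to change.** Before unblinding, in 9.4.2 and 9.4.3 or in the promised statistical analysis plan, add three named covariates:

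- baseline NEWS2;
- corticosteroid started before randomisation (yes/no);
- remdesivir started before randomisation (yes/no).

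Use pre-randomisation values only. Section 6.5.1 collects medications from admission through Day 28, so the two drug indicators must be defined by start time relative to randomisation, including for drugs started on Day 1. Treatment begun later can follow from the course of illness and should not enter as a baseline covariate. Add baseline oxygen requirement only if it is recorded in graded form.

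Optionally, add one descriptive row to 9.4.7 (corticosteroid and/or remdesivir before randomisation vs neither), stating that its interaction test has low power.

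The cost is three model terms and, if used, one subgroup row. The primary test, alpha, sample size and patient management do not change. The case report form is not among the documents, so the coding of these variables should be confirmed first.

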The primary objective of the VA CURES program is to evaluate the clinical efficacy of different investigational therapeutics compared with the control arm by binary analysis of the composite primary outcome of acute hypoxemic respiratory failure or all-cause death by Day 28. Acute hypoxemic respiratory failure is defined as the initiation of mechanical ventilation [either via

endotracheal intubation or as non-invasive positive pressure ventilation (NIPPV) for an indication other than for pre-diagnosed sleep apnea at outpatient settings] OR extracorporeal membrane oxygenation (ECMO).

The secondary objectives are to evaluate the clinical efficacy and safety of different investigational therapeutics compared to the control arm as assessed by the secondary efficacy outcomes and the safety outcomes defined in the stage-specific Objectives and Endpoints. Each stage may prioritize different secondary endpoints for the purpose of multiple comparison analyses.

Study Outcomes

Primary efficacy outcome: Proportion of participants developing acute hypoxic respiratory failure or all-cause death up to day 28.

Key secondary efficacy outcome: Time to recovery (as determined by attaining a score of 1,2 or 3 on the World Health Organization (WHO) 8-point ordinal scale).

Study Population

This trial will study putative therapeutics in a hospitalized adult population (≥ 18 years old) with moderate to severe COVID-19. The trial will have common inclusion and exclusion criteria but may be modified for each stage for the unique risk of the study product in that stage.

Inclusion Criteria

- 1) Age 18 or older.
- 2) Confirmed acute SARS-CoV-2 infection.
- 3) Requirement for supplemental oxygen therapy that is either new or at least 2 Lpm greater than previous outpatient chronic therapy.
- 4) Ability to provide written informed consent from patient or legally authorized representative (LAR).

Exclusion Criteria

- 1) anticipated hospitalization <48 hours.
- 2) anticipated respiratory failure (as defined above) or death within 48 hours.
- 3) Septic shock or multiple organ dysfunction or failure.
- 4) Current or anticipated participation in another randomized trial for SARS-CoV-2.

Study Phase

Phase 3

Study Sites

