7.2 PARTICIPANT DISCONTINUATION/WITHDRAWAL FROM THE STUDY

Participants are free to withdraw from full participation in the study at any time upon request, without any consequences.

If a participant requests to be withdrawn from the study, the LSI or delegatee may offer the participant an option of limited participation. The two limited participation options that may be offered are:

1. A participant can choose to withdraw from receiving study product, but agree to all other follow-up, including study staff contact and laboratory testing.

OR

2. A participant may choose to withdraw from direct participation in all study activities but allow ongoing medical records review by study staff (no contact).

A participant may also choose to withdraw completely from all study activities. If a participant fully withdraws consent, no study procedures may be performed, and no more data may be collected as of the time point at which the patient withdrew consent.

In any of the situations above, study personnel will ascertain and clearly document in the EHR any limits to ongoing participation. A participant's usual medical care is not affected by whether study participation continues (fully or to a lesser degree) or ends.

If a participant withdraws consent or is withdrawn from the study by the Local Site Investigator (LSI), an Early Termination Form will be completed. Data collected up to the point of withdrawal will be used in the analyses. If a participant agrees to limited participation the site must complete a Reduced Participation form.

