2.3 POPULATIONS FOR ANALYSES

The primary analysis will be based on an intention-to-treat population, including all participants randomized. The safety analysis will be based on a modified intent-to-treat population consisting of all participants who received at least one dose of any study intervention.

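### Excluding participants without the Day-28 outcome selects on the outcome: it typically raises both event proportions, and it biases the treatment difference when loss differs between arms

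*Combined protocol and SAP*

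**What the plan says.** The statistical sections carry numbers 9.x in the table of contents and 2.x in the body; the contents numbering is used here.

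- **Endpoint (1.1 Synopsis):** "Proportion of participants developing acute hypoxic respiratory failure or all-cause death up to day 28". It is binary and is reached at the first qualifying event.
- **Population (9.3):** "The primary analysis will be based on an intention-to-treat population, including all participants randomized".
- **Missing outcome (9.4.2):** "subjects without the primary outcome data will be excluded from the primary analysis". The test is a chi-square on those who remain.
- **Sensitivity (9.4.2):** "Sensitivity analyses will evaluate the impact of making different assumptions about missing observations and use analysis methods such as multiple imputations". Details are left to a statistical analysis plan.
- **Withdrawal (7.2):** "Data collected up to the point of withdrawal will be used in the analyses". After full withdrawal, "no more data may be collected as of the time point at which the patient withdrew consent". A participant may instead agree to records review without contact, which can still recover the outcome.
- **Amount (9.2):** the sample size allows for 5% missing primary outcomes. This is one overall figure, with none by arm.

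No section says when the primary outcome counts as missing.

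**The concern.** An analysis that drops participants is not on all participants randomised, so 9.3 and 9.4.2 cannot both describe the primary analysis.

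The way people are dropped matters more than the label. A participant who is ventilated or dies on Day 5 and is lost on Day 10 has a known outcome and stays in. A participant who is event-free on Day 10 and then lost is removed, along with ten known event-free days. Whether a lost participant is counted therefore depends on whether the event came first. Random loss does not protect against this, because the selection arises from the rule itself.

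At stake are the reported event proportions and, where loss differs between arms, the risk difference and the error rate of the headline test. The interim efficacy and futility looks concern the same primary endpoint.

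**Working it through.** **Inputs from the documents.** Event proportions 30% and 20%; two-sided 0.05; 666 evaluable and 702 randomised, 1:1, so 351 per arm; 5% missing overall. **Assumptions, not in the documents:** loss by arm, time of loss, time of events, and the Day-28 risk of those lost.

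**1. The plan's own figure.** The plan describes its table as "using the z-test with a two-sided significance level = 0.05 and assuming no missing data". With unpooled variance:

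n per arm = (1.960 + 1.036)² × (0.30×0.70 + 0.20×0.80) / 0.10² = 8.978 × 37 = 332.2, so 333 per arm and 666 in total.

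666/0.95 = 701.05, so 702. Both figures reproduce. (The text prints the inflation as 702/0.95, a typing slip.)

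**2. Effect of deletion.** Let p be an arm's true Day-28 risk, m the share with a missing outcome, and q the true Day-28 risk among those missing. The complete-case proportion is

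r = (p − m·q)/(1 − m), so r − p = m(p − q)/(1 − m).

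The direction depends only on whether q is below or above p. If loss is non-informative, q is below p, because the lost have already passed some days without an event.

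**3. Non-informative loss, simulated** (events at a constant rate or mostly early; true control rate 30%):

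| Share missing | Complete-case | Kaplan-Meier at Day 28 |
|---|---|---|
| about 3% | 30.4-30.8% | 29.9-30.0% |
| about 7-8% | 31.1-32.1% | 29.9-30.0% |

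At about 4-5% missing, with true rates of 30% and 20%, complete-case gives 30.7-31.2% and 20.5-20.9%. The difference is 10.2-10.3 points, so it barely moves.

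**4. Equal loss of 5% per arm, by formula.**
- q = 0: 0.30/0.95 = 31.6% and 0.20/0.95 = 21.1%; difference 10.5 points.
- q equal to the arm's own risk: no change.
- q = 50%: (0.30 − 0.025)/0.95 = 28.9% and (0.20 − 0.025)/0.95 = 18.4%. Both rates fall.
- No true effect (30% in both arms, same q): r is identical in the two arms, the difference is zero, and two-sided error stays at 5.0%.

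**5. Unequal loss, no true effect** (7% control, 3% plasma; 351×0.93 = 326.4 and 351×0.97 = 340.5 analysed). One-sided error favouring plasma = 1 − Φ(1.96 − d/SE), where d is the false difference:

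| q in both arms | Control r | Plasma r | d (points) | SE (points) | One-sided error |
|---|---|---|---|---|---|
| 0% | 0.30/0.93 = 32.3% | 0.30/0.97 = 30.9% | 1.3 | 3.60 | 5.6% |
| 15% | 0.2895/0.93 = 31.1% | 0.2955/0.97 = 30.5% | 0.7 | 3.58 | 3.8% |
| 30% | 30.0% | 30.0% | 0 | 3.55 | 2.5% |

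With the imbalance reversed (3% control, 7% plasma), true rates of 30% and 20%, and q = 0, the rates are 0.30/0.97 = 30.9% and 0.20/0.93 = 21.5%. The difference shrinks to 9.4 points, and power is about 79-80% against the planned 85%.

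**6. Kaplan-Meier when loss is informative** (7% against 3%, no true effect, the lost never have an event). Its false difference is within about 0.1 point of zero if events fall mostly in the first 10 days and losses in Days 8-27. It is 0.6 points if events are evenly spread, 0.6-1.1 with losses in Days 1-7, and 0.9-1.15 with losses in Days 1-3, where complete-case gives 1.2-1.3. It helps in every case, but it is not unbiased.

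**The case against.** The exclusion is stated openly, with a 5% allowance in the sample size and sensitivity analyses planned, including multiple imputation. Time to death or respiratory failure by Day 28 is already a secondary endpoint with Kaplan-Meier curves, so the event-free days are used somewhere. Records review can recover outcomes. The trial is double-blind, and nothing in the documents predicts unequal loss. All of this stands, and it limits the likely size. It does not repair the primary test, because the secondary and sensitivity analyses leave the headline estimate and p-value on the deleted set.

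Four stronger readings are tempting, and the documents do not support them.

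- **That both event proportions must be overstated.** The missing are event-free when last observed, not at Day 28. After full withdrawal their later course is unknown. People lost while deteriorating would push the rates down.
- **That type I error is generally lost.** With equal loss, and equal risk among the lost, it holds. The 5.6% figure needs both 7% against 3% loss and every lost participant event-free to Day 28.
- **That Kaplan-Meier removes the bias.** It does so only if censoring is non-informative; step 6 shows how far the result depends on timing.
- **That 7.2 contradicts 9.4.2.** The two are compatible if events before withdrawal count, which is the natural reading. The conflict is between 9.3 and 9.4.2.

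**Conclusion.** The concern holds in conditional form. The primary analysis described in 9.4.2 is not the all-randomised analysis promised in 9.3, and its deletion rule selects on the outcome even when loss is random. The event proportions are typically inflated, and whether they are depends on the lost having lower Day-28 risk than their arm. The treatment comparison is at risk mainly if loss is unequal. Over the range examined, one-sided error runs from the nominal 2.5% up to 5.6%, and a true 10-point benefit can shrink to 9.4.

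These results rest on reading a missing outcome as one not yet reached at last observation, and on assumed loss patterns for which the documents give no figures by arm. If loss stays at or below 5% and balanced, the practical effect is modest. The change is still worth making, because the direction of the bias cannot be known in advance and a better primary estimate is within reach of data already collected.

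**What to change.** 1. Define a missing primary outcome in 9.4.2, and state that any event before loss or withdrawal counts as an event.
2. Make the primary estimate and test the Day-28 risk difference on all randomised participants. Use either Kaplan-Meier with censoring at last contact or the multiple imputation already planned. Imputation must start from the last observed state and day: a model using baseline data alone would give the lost roughly the complete-case risk and reproduce the problem.
3. Move the complete-case chi-square to a sensitivity analysis, and bring 9.3 and 9.4.2 into agreement.
4. Report missingness by arm, with a tipping-point analysis over the Day-28 risk of the lost in each arm.

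**Cost.** Wording in the protocol and analysis plan, and a little more programming. Clinical status is already recorded daily in hospital and collected at follow-up, and the target of 702 need not change. The interim boundaries are on the z-scale, so the estimate divided by its standard error can be used with them. The price is a non-informative-censoring (missing-at-random) assumption. Because Kaplan-Meier is biased when loss is informative, item 4 is a necessary part of the change.
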